### Intervention schools

- Rationale for the selected intervention- Based on the preliminary positive data for MI with minority youth, the acceptability of an MI approach by health care providers, and the promising foundational outcomes from the PI’s R21 (ACTION), this study will utilize MI for both the prevention component (discussing BMI results) as well as the treatment component of this study (ACTION weight management program).
- Training in and monitoring of MI- All interventionists will be SBHC clinicians from the intervention schools. The goal of MI is to bolster and support youth’s internal motivation, autonomy, and self-efficacy to enact positive behavioral choices, which have been observable up to twelve months post-intervention. In line with the approaches of MI, all interventionists will be taught to utilize MI with adolescents to support and promote the selection of healthier food options and to consistently engage in physical activity for maintenance or achievement of a healthy weight. Consistent with her role across five prior NIH-funded R01s and R03s, Co-I [name] will oversee the training and supervision of MI providers to ensure intervention integrity and fidelity. To that end, all interventionists will be trained using the following five steps. Interventionists will (1) begin their training with an in-person MI training (2 days), which will include interactive training (didactic and role playing) on the use of MI, (2) be required to read the study manuals, (3) pass a knowledge test to evaluate their grasp of the concepts within and behind MI (e.g., with a pass rate of at least 80% on the fidelity checklist and 100% adherence to essential therapeutic elements), (4) watch a MI intervention session with a pilot participant and discuss the details of the session, and (5) conduct two pilot sessions, during which Co-I [name] will evaluate interventionists’ proficiency in MI, with an eye to the following MI integrity components (e.g., MI spirit, MI consistent behaviors including use of reflections, demonstration of accurate empathy, minimal to no closed questions, minimal to no advice without permission). As delineated in the adolescent assent and parent consents, all visits with the adolescent patient will be audio taped to facilitate the continuous monitoring of fidelity of the intervention. All interventionists will participate in once per week teleconference-based supervision, during which randomly selected tapes will be reviewed by [name], who will provide feedback and coaching to the providers. This approach also facilitates continuing performance review, minimization of drift, and a venue to discuss potential problems that might arise in conducting MI-based interventions. We utilize this thorough, multi-level training approach because providers who receive coaching after the initial training are more likely to fully retained clinical trial proficiency levels with MI when compared to those who receive only workshop training.
- Prevention intervention (discussing BMI results/healthful eating/physical activity)- All youth in intervention schools will participate as follows: 1) SBHC providers will use BMI obtained by the data collection team to discuss BMI results directly with adolescent participants. This visit will be a standard part of each 9th or 10th grade student’s start-of-school year health visit; 2) all providers in the intervention schools will use MI-based approaches throughout this discussion to support and enhance adolescent’s healthy eating and physical activity behaviors; 3) consonant with prior data indicating that youth have questions around how to select healthier foods and AAP recommendations, all youth will be invited to actively engage in a discussion around how adolescents can maintain or achieve a healthy weight; 4) finally, all parents of intervention school students, regardless of BMI, will be sent a letter describing their children’s BMI results and AAP recommendations. Annual BMI results, healthful eating and physical activity for healthy weight will be discussed each year. For students with BMI  $\geq 85^{\text{th}}$  percentile (defined as overweight or obese), this will be the first interaction with SBCH providers. At the end of the discussion (steps 2-3), SBHC providers will schedule the student’s first meeting for the weight management intervention after summer.

- Treatment intervention (ACTION weight management program)- Participants with BMI  $\geq 85^{\text{th}}$  percentile (overweight/obese) at baseline will receive ACTION. Consistent with our approach in our NIH-funded pilot study, prior to their first session of ACTION, adolescents will be scheduled by the data collection team in the SBHC for fasting blood sampling to evaluate for impaired fasting glucose, insulin resistance and dyslipidemia. SBHC providers will review these results at the youth's first session of ACTION. Session 1 will begin with SBHC clinicians providing youth with an educational DVD on nutrition and physical activity. At this time, using MI-based approaches (e.g., emphasis on autonomy, support of self-efficacy) clinicians will review pertinent physical exam and laboratory findings with the adolescent, assess the adolescent's dietary and physical activity behavior, provide feedback about how their diet and activity compare to national recommendations, and elicit the participant's over-all response to this information. Next, providers will invite adolescents to discuss barriers to healthier eating and physical activity, as well as general and personal strategies that might be helpful in overcoming these obstacles. For youth who are not yet ready to engage in discussions about change, providers will openly and supportively explore ambivalence about dietary and physical activity change, with an eye to supporting autonomy and self-efficacy around behavior change. For youth who are interested in exploring a change behavior, as indicated by their change talk; providers will help youth identify and develop 1-2 strategies for enacting positive behavior changes for the upcoming weeks (in the interim between ACTION sessions). These plans might include topics such as how and when to conduct physical activity, and how and where to purchase healthy foods. Because of the broad-based consensus that long-term interventions are needed for long-term behavioral change across pediatric nutrition and physical activity, and based on our R21 outcomes, we propose doubling our prior ACTION intervention (8 sessions/1 year) to yield a total of 16 sessions (e.g., 8 sessions per academic year for two years). This type of approach is uniquely possible due to the close proximity that SBHCs have to participating youth.

Another advantage of SBHCs is their on site location (school) which adds convenience for students and caregivers. Students are already at school and the caregivers do not have to leave work to bring their adolescent child to the clinic. However, because caregivers usually do not accompany the adolescent to the SBHC clinic visit, family and parental involvement is limited. Our formative findings in our NIH-funded pilot indicated that parents and adolescents both wanted some involvement of parents throughout the intervention. To increase caregiver involvement in ACTION, telephone contact will be made with the caregiver after each clinic visit to update them about their child's progress. In addition, a caregiver newsletter containing obesity risk reduction strategies will also be given at the beginning of the intervention. The purpose of the newsletter is to help caregivers create a more health-promoting home environment, so as to effectively support their adolescent child in improving nutrition and physical activity. This approach was pilot tested in the R21 study.

To improve convenience and access, we will also use telemedicine, through a secure, web-based, pass-coded network as a way to carry out motivational interviews for intervention participants. This mode of contact will be used in situations where it is not possible for the student and provider to attend the clinic for their in-person scheduled visit. To ensure privacy, telemedicine will be done in school-based health center exam rooms behind a closed door in the same way that in-person visits will be conducted.

#### Comparison schools

- Parent notification of results only- Annual BMI results collected by the data collection team will be sent to parents/caregivers with AAP obesity prevention recommendations. Students in the comparison schools will not receive discussions about their BMI results, healthful eating and physical activity. Consistent with standard of care, students with BMI in the overweight or obese category will be scheduled by the data collection team for fasting blood insulin, glucose, hemoglobin A1c and lipid tests in the SBHC. The BMI and laboratory blood results of overweight/obese students will be sent to their parents/caregivers with a recommendation to follow-up with their school's SBHC or their primary care provider. Annual BMI results (and laboratory blood results if the student is overweight/obese) will be mailed to parents at the same points in time for both the intervention and comparison schools.

ii) Describe methods by which data will be managed - stored and destroyed.

Only research team members have access to study information. Students will be given unique identifiers so that names will not be used on data collection instruments or during data entry. Students names with their unique

identifiers will be kept in only one place in their study charts so that the team can ensure that they have the correct participant before starting data collection. Links will be kept until all data entry and analysis are completed. Data will be stored in locked file cabinets in the PI's research space in the UNM Prevention Research Center. Electronic data will be stored on a password protected computer. REDCap, a secure, web-based application from the UNM CTSC, will be used to for building and managing databases. REDCap access will be restricted to PI and research team. For intervention overweight and obese students attending the SBHC weight management program, visits will be kept separately from their SBHC medical records in a locked file cabinet used specifically for the project. All audio recordings will be securely destroyed within 3 years of study completion. Destroying data will follow HIPAA regulations, 6 years after HRPO acknowledged of study closure.

iii) Describe methods by which data will be analyzed and interpreted. Include the following, if applicable:

- **Process measures and analysis:** The purpose of process evaluation is to accurately describe the implementation of measures and the intervention, to assess the quality and consistency of measurement and intervention implementation (fidelity), and to document the extent of participant exposure to the intervention (reach and dose). Process evaluation data will be collected continuously from the intervention schools as follows: 1) MI training and monitoring will include training attendance log and evaluation forms from interventionists at MI training sessions; and weekly teleconference supervision for intervention providers. 2) BMI result/healthful eating/physical activity discussions with students will include tracking attendance of students. 3) Referral of overweight/obese students to the SBHC weight management program will include tracking the number of overweight/obese students referred by the number eligible for referral. 4) The ACTION program will include student attendance; length of clinic visit; content of visit; receipt of materials (as reported by students) and use of toolkit handouts (as reported by providers); parent phone contact by providers; and parent receipt of newsletter and toolkit handouts. We will conduct mid-year monitoring on these process measures to ensure intervention fidelity and adjust accordingly if participant exposure is lower than expected. If we determine that any component is not occurring as planned, we will immediately address these inconsistencies with the appropriate personnel.
- **06.16.14 A Doctor of Nursing Practice project will evaluate Session 1 MI-based intervention discussions:** assess adolescent satisfaction with Session 1 MI-based discussions and explore perceived primary care provider (interventionist) comfort with Session1 MI-based discussions using the MI Participant Satisfaction Survey and MI Provider Self Assessment Survey evaluation forms as part of process and program evaluation. However, all of the sessions will be evaluated by the ACTION PAC team.

**Sample size and power analysis:** Given that incidence of overweight/obesity after 2 years (percent of students who were not overweight or obese at baseline but who become overweight or obese) is the primary outcome for the prevention intervention (discussing BMI results/healthful eating/physical activity with students using MI) (**Hypothesis 1a**), calculations are based on the ability to detect a 7.4% incidence difference between the intervention and comparison schools as previously reported from a policy-based school intervention to prevent overweight and obesity. Recruitment of 120 students per school with ~36% who will be overweight or obese and ~64% who will not be overweight or obese (estimated from our previous experience) will give us a total sample of 960 students. Student retention rates in the proposed schools from 9th – 11th grades and from 10th – 12th grades range from 52% to 92% (mean of 72%). In our previous R21, 5% dropped out of the study and 8% left school. Taking into account the schools' retention rates and also our small dropout rate from our previous NIH-funded R21, we are using 35% as the potential attrition rate to calculate a sufficient sample size for testing: 1) BMI result/healthful eating/physical activity discussion with MI component, and also for 2) the weight management component. ~77 students per school are anticipated to be <85th percentile (120 students × 64% who are <85th percentile). If there is 35% attrition, ~50 students per school (400 total) will be available to calculate incidence of overweight/obesity. Based on analysis of our NIH-funded R21 study at two high schools, we used a value of 0.01 for the intraclass correlation (ICC). Therefore, with two-tailed alpha of 0.05 and power level of 0.80, differences of 6% to 10% will be detectable if incidence from the comparison schools range from 7% to 15%, respectively.

Due to higher than anticipated attrition at the high schools from baseline to 1st annual measurements, we will increase our current total sample enrollment (n=960) by 5%, to give a new total sample of 1008 participants.

For (**Hypothesis 1b**) pre-post measurements of our secondary outcomes (physical activity and dietary intake of sweetened beverages, fat, whole grains, and fruits and vegetables which are continuous variables), we will analyze students with  $\text{BMI} < 85^{\text{th}}$  percentile and students with  $\text{BMI} \geq 85^{\text{th}}$  percentile separately. For students with  $\text{BMI} < 85^{\text{th}}$  percentile, assuming 35% attrition (400 total), ICC of 0.01, two-tailed alpha of 0.05 and power level of 0.80, we will be able to detect an effect size of 0.41, which falls between a small to medium effect size as defined by Cohen. For students with  $\text{BMI} \geq 85^{\text{th}}$  percentile, assuming 35% attrition (224 total), ICC of 0.01, two-tailed alpha of 0.05 and power level of 0.80, we will be able to detect an effect size of 0.51, which is a medium effect size as defined by Cohen.

For (**Hypothesis 2**) the treatment intervention primary outcomes, ~43 students per school are anticipated to be overweight or obese (120 students  $\times$  36% who are  $\geq 85^{\text{th}}$  percentile). If there is 35% attrition, ~28 students will have  $\text{BMI} \geq 85^{\text{th}}$  percentile (overweight or obese) per school (224 total) and be available to calculate difference in BMI z score and insulin resistance (HOMA-IR) after two years. Therefore, we will have 84% power for detecting a difference of 0.16 in two-year BMI z score change between the intervention group and the comparison group. BMI z score change of 0.16 was the change documented in a high intensity ( $>75$  hours of contact) obesity intervention that was cited in the most recent Cochrane review and an evidence report prepared for the US Department of Health and Human Services as one of the best outcomes of intensive lifestyle interventions in children and adolescents. Using data from this study, we will have 80% power to detect a 27% change between the intervention and comparison groups for HOMA-IR.

Analysis Plan: As a preliminary step, we will examine the skewness and kurtosis of all variables to assure no problematic deviations from normality. In the event of such deviations, we will use appropriate transformations or use non-parametric methods. Analyses will be conducted using SAS Version 9.3, STATA Version 12 and Mplus Version 5. All programs include capabilities to test models with categorical outcomes, missing data, and to account for a design that uses a multilevel or clustered framework.

- Pretest equivalence: To explore the possible size and direction of bias that may exist, the pretest equivalence of conditions across demographics, BMI percentile, and other outcome variables of interest will be assessed via t-tests on continuous items and  $\chi^2$  tests of categorical items from the pretest. Wilcoxon rank sum tests or appropriate transformations will be used for non-normal data. We will use the Bonferroni approach to correct for alpha inflation with an experiment-wise alpha of 0.05. For variables where there are significant differences, the baseline values will be included as covariates in the analysis of intervention effects.
- Analysis of intervention effects: Analyses will be conducted in a multilevel framework to account for clustering within schools. Mixed effects linear regression (SAS Proc Mixed) will be utilized for continuous outcomes (e.g., minutes of moderate or vigorous physical activity, BMI z score) and the generalized estimating equation approach (SAS Proc Genmod) will be used for binary dependent variables (e.g., hypertriglyceridemia, prediabetes defined by glucose and hemoglobin A1c) to study intervention impact on physical, behavioral and biochemical outcomes after 2 years. The following main outcomes of interest will be assessed: (**Hypothesis 1a**) Incidence of overweight and obesity after 2 years among students who were not overweight or obese at baseline; (**Hypothesis 1b**) sweetened beverage consumption, fat intake, fruits and vegetable intake, whole grain consumption, and time in moderate and vigorous physical activity after 2 years; (**Hypothesis 2**) BMI z score and HOMA-IR (insulin resistance index score) after 2 years among those students who were overweight or obese at baseline. Additional outcomes that will be assessed in the cohort of students who are overweight or obese at baseline include waist circumference, percent body fat, blood pressure percentiles, and biochemistries (glucose, insulin, hemoglobin A1c, and lipids) after 2 years. Hypotheses will be tested at a 0.05 significance level, two sided. Descriptive statistics (e.g., means  $\pm$  SD, percentages) will be used to evaluate process data. Bivariate relationships of participants' BMI z score change to student attendance will be assessed in the intervention group and a multivariate analysis will be subsequently used to control for other demographic variables. An intention to treat analysis plan will be used. To that end, adolescents who complete a fraction of the sessions will still be accounted for in the analyses. Data imputation methods will be used for missing data. Additionally, we will assess number of sessions completed to determine how attendance is associated with outcomes. The study will assess BMI trends in NM using data from the Youth Risk Resiliency Survey (the NM version of the CDC's Youth Risk Behavior Survey) to evaluate secular trends. The study will use the school's demographic data on race/ethnicity, age, and free/reduced lunch meals to assess the representativeness of the recruited population. If the recruited population does not appear to be representative, we will use weighted data

analysis procedures to estimate outcomes for the school population.

Baseline values will be included as covariates in the mixed effects linear regression models for continuous dependent variables and the generalized estimating equation models for binary dependent values including the incidence of overweight or obesity or the presence or absence of specific components of the metabolic syndrome. For students who repeat grades, we will include "repeated grade" as a covariate. Intervention (coded 0=control and 1=intervention) will be entered as a fixed effect into the multilevel models predicting outcomes. One equation will be estimated for each of the outcomes of interest. This approach is conceptually identical to an analysis of variance or covariance (ANOVA or ANCOVA) but has two distinct advantages. First, it allows for the analysis of clustered data, and second, it avoids list-wise deletion of subjects with missing assessments. The model relaxes the restrictive assumption that the data are missing completely at random and provides unbiased estimates under the less restrictive assumption of missing at random. This approach to missing data, i.e., the use of techniques that include full information maximum likelihood estimation of missing values, will be used.

• **Analysis of semi-structured Interviews (Aim 3):** Parent and student interviews conducted following the intervention will be analyzed using standard qualitative assessment methods. [name] will lead this analytic process. The interviews will each be transcribed and distributed to the research team. Each member will review transcripts independently, identifying themes related to the stem questions as well as other emergent areas of interest. The analysis will proceed in an iterative fashion, with the team reviewing sets of 3 to 4 transcripts in each category (parent and student). Following the independent reading, the team will meet to list the full range of themes, identify anomalous or unanticipated findings, and revise the interview guides accordingly. This process will continue until the team has reached consensus. At that stage, the thematic list will be converted into a template for coding purposes. Interviews will be coded in NVivo 9 (Melbourne, Australia), a qualitative data analysis software package, at which point queries to refine analytic and interpretive understandings will be conducted.

06.16.14 As part of process and program evaluation, a Doctor of Nursing Practice program evaluation project will include data analysis of Session 1 MI-based intervention discussions to assess adolescent satisfaction with the MI-based discussions and explore perceived provider comfort with MI using the MI Participant Satisfaction Survey and the MI Provider Self Assessment Survey evaluation forms. However, all of the sessions will be evaluated by the ACTION PAC team.

iv) Specific description of any experimental drug, device, or procedure. Any substance or instrument to be used in or on humans which has not received FDA approval for the proposed use requires an IND, IDE, or approval of the Radioactive Drug Research Committee.

v) Specific description of any use of biological samples. This is to include their origin, links to identifying information, storage, access, and future use.

Biomarkers include insulin, glucose, hemoglobin A1c, and lipids will be obtained in overweight/obese adolescents. Samples will be drawn by venipuncture. Serum samples will be allowed to clot. All samples will be centrifuged on-site and transported in an ice chest with freezer packs to Tricore Laboratory ([name]) or Tricore in Las Cruces for processing. We will not put names on tubes with blood; instead, the tubes will receive a unique identification number that will be used to identify the blood. No blood will be stored for future use.

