## V. Experimental Design and Methods:

- i) Provide concise description of experimental design and procedures to be used to accomplish study goals. Include precise descriptions of all tests and measurements, and their expected duration. Include optional testing and blinding/un-blinding procedures if applicable.

Research Design: A cluster randomized control trial will be used to test hypotheses. The NM Department of Health, Office of School and Adolescent Health provided a list of recommendations for schools with functioning SBHCs serving a large Hispanic student population. PI [name] successfully approached these schools about collaborating on the proposed research; they agreed (see Letters of Support). To limit the possibility of confounding effects, our collaborating high schools all share the following four characteristics: 1)

Enrollment/ethnicity: At least >700 enrolled students, with at least 40% Hispanic youth, 2) Environmental resources: at least one outdoor field, one gymnasium, and physical activity opportunities, 3) Food service resources: at least one cafeteria, competitive foods (foods brought into schools from outside vendors), and vending machines, and 4) a functioning SBHC. To further control for plausible alternative explanations of outcomes between groups, pretest differences will be compared between groups. The pretests will allow exploration of the possible size and direction of bias that may exist. Thus, the joint use of a pretest and a comparison group will allow examination of possible threats to validity (see Analyses). Assessments will be conducted at pretest (baseline) and annually for two more years (see Table 1). The assessment time waves will allow us to follow 9th grade students annually until their 11th grade year and 10th grade students until their 12th grade year.

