Data Collection Measurements: All measures will be collected in both intervention and comparison schools. Protocols with standardized procedures and quality control procedures will be followed by research staff to ensure accuracy, precision, and completeness of data collection. Training for data collection team members will be given by [name], MS (for physical activity related measures) and by [name] (for anthropometrics and nutrition related measures). Each year, before measurements begin, these investigators will retrain and certify the data collection team in all measures. Demographic, physical, dietary intake and physical activity data will

be collected at baseline (pretest), at one year (intermediate), and at 2 years (follow-up) in both intervention and comparison schools. These time intervals will allow us to assess pretest to posttest changes on hypothesized outcomes, and intermediate effects of the intervention. Students will be reimbursed \$20 per measurement wave (total possible=\$60); compensation is consistent with other clinical trials in NM.

- Demographic information to be collected on participants and their parents include age, sex, socioeconomic status, education, and race/ethnicity, using our previously developed Health History Survey. Our Health History Survey also includes questions on family history of type 2 diabetes (first and second degree relatives), chronic medical conditions, and current medications.

A follow-up health history will be administered at intermediate (year one) and follow-up (year two) measurement periods. Participants will update contact and health information. Participants will be excluded at intermediate and follow-up measurement periods if they are pregnant or have been diagnosed with an eating disorder.

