- Biomarkers include insulin, glucose, hemoglobin A1c, and lipids will be obtained in overweight/obese adolescents. Samples will be drawn after an ten hour overnight fast. Serum samples will be allowed to clot. All samples will be centrifuged on-site and transported in an ice chest with freezer packs to Tricore Laboratory for processing. Insulin resistance will be calculated using the homeostatic model assessment insulin resistance index [HOMA-IR = (Product of fasting insulin mU/L and fasting glucose mmol/L)/22.5] which has been shown to have reliable sensitivity and specificity in assessing insulin resistance. HOMA-IR increases with increasing insulin resistance.
- Dietary intake will be assessed by the Block Food Screener 2007 a validated food frequency questionnaire. This self-administered tool estimates an individual's usual intake over a period of 1 week. NutritionQuest (Berkeley, CA) will create the data base from the completed surveys for analysis.
- Physical activity will be assessed using the 3-Day Physical Activity Recall (3DPAR) and accelerometry. The 3DPAR has established instrument validity in adolescents based on concurrent observation with motion sensors. Objective assessments of physical activity will be obtained using the ActiGraph GT3X accelerometer (Shalimar, FL). The Actigraph has documented evidence of validity and inter-instrument reliability in children and adolescents. Consistent with previous studies, monitors will be attached to adjustable elastic belts and worn over the right hip during waking hours for 7 consecutive days. Accelerometer counts will be uploaded to a customized EXCEL macro written by [name] for determination of daily time spent in sedentary, light, moderate, vigorous, and moderate-to-vigorous physical activity. The age-specific count thresholds corresponding to these intensity levels will be derived from the MET prediction equation developed by Freedson and co-workers as published by Trost and colleagues and replicate the intensity categories used in population-representative objective monitoring studies (e.g., NHANES).
- We will assess change using readiness to change (casaa.unm.edu), sedentary behavior (Robinson, 1999), eating attitudes (Garner et al, 1982) and health related quality of life (Varni) by evaluating adolescents' status on these measures at assessment waves.

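### Could two-year HOMA-IR be missing for students whose BMI falls below the 85th percentile, because bloods follow current weight status?

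*Combined protocol and SAP*

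**What the plan says.** Who is sampled:

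- The biomarker item under Data Collection Measurements says "Biomarkers include insulin, glucose, hemoglobin A1c, and lipids will be obtained in overweight/obese adolescents". Section V.v (biological samples) repeats it: "will be obtained in overweight/obese adolescents. Samples will be drawn by venipuncture". Neither gives a time point.
- Comparison schools has students in the overweight or obese BMI category scheduled for fasting bloods, again with no time point. It then says of both arms: "Annual BMI results (and laboratory blood results if the student is overweight/obese) will be mailed to parents".
- The ACTION paragraph under Intervention schools opens with students at or above the 85th percentile at baseline and schedules their fasting bloods before session 1. This is the only draw with explicit timing.
- The sentence listing what is collected at all three waves begins "Demographic, physical, dietary intake and physical activity data will" and does not name biomarkers. The same paragraph says all measures are taken in both arms. Research Design places assessments at baseline and "annually for two more years (see Table 1").

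Who is analysed:

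- Sample size and power analysis (Hypothesis 2) takes about 28 students per school, 224 in total, to "be available to calculate difference in BMI z score and insulin resistance (HOMA-IR) after two years".
- Analysis of intervention effects names "BMI z score and HOMA-IR (insulin resistance index score) after 2 years among those students who were overweight or obese at baseline". The other blood measures after two years fall under "Additional outcomes that will be assessed in the cohort of students who are overweight or obese at baseline".

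Missing data: the analysis plan states intention to treat, imputation, one equation per outcome with baseline covariates, and full-information maximum likelihood under missing at random. Separately, Data Collection Measurements excludes students at years 1 and 2 who are pregnant or have a diagnosed eating disorder. Sections VI.iii and VI.vii call pregnancy a withdrawal criterion.

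**The concern.** The analysis set is fixed at baseline, while the sampling wording could be read as following current status. On that reading, year-2 BMI decides who has a year-2 HOMA-IR. Crossing below the 85th percentile is what ACTION aims for, so the intervention arm would lose more values, and they would come from students who responded. A HOMA-IR equation with baseline covariates only does not contain year-2 BMI, so its missing-at-random claim would not cover this loss. The effect on a primary outcome would be understated and power reduced, and values not drawn at year 2 cannot be recovered.

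The exclusions at years 1 and 2 raise a smaller question. They occur after randomisation, and the intention-to-treat text explains only partial session attendance. It does not say how these students enter the analysis, or whether a student pregnant only at year 1 supplies the two-year outcome.

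**Working it through.** **1. The plan's own figures.** 120 × 0.36 ≈ 43 per school; 43 × 0.65 ≈ 28; 28 × 8 = 224. With ICC 0.01 the design effect is 1 + 27 × 0.01 = 1.27. The standard error in SD units is √(1.27 × 2/112) = 0.150. A t-test on 6 df (8 schools less 2) with 80% power detects 0.507, against the stated 0.51. The same method for 400 students gives 0.411, against the stated 0.41. The stated power therefore uses the whole baseline-defined cohort, with no allowance for unsampled improvers.

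**2. Which reading the text supports.** For baseline status: the count of 224, the two-year HOMA-IR cohort, the two-year biochemistry cohort, and the ACTION paragraph's draw. For current status: no statement about drawing, only a present-tense condition on what is mailed. The remaining sampling sentences are silent on timing. Table 1, where the schedule is said to be, is not in the text available for this review, so no omission can be inferred from it.

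**3. Size if current status were followed.** The documents give no SDs, so these inputs are assumed:

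- Baseline z uniform from 1.04 (the 85th percentile) to 2.40 or 2.80, so width w = 1.36 or 1.76.
- SD of z change 0.30, 0.36 or 0.41. These are back-solved from the stated 84% power for 0.16 with 112 per arm: t on 6 df, normal, and normal without a design effect.
- SD of log HOMA-IR change 0.6; correlation with z change 0.2 to 0.5.
- Treatment effects 0.16 in z and 27% in HOMA-IR (ln 0.73 = −0.315).

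Let k = 0.16/SD.

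- Missing, comparison: SD × 0.399/w. Missing, intervention: (0.16 Φ(k) + SD φ(k))/w.
- At SD 0.30, w = 1.36: 0.30 × 0.399/1.36 = 8.8%; (0.16 × 0.703 + 0.30 × 0.346)/1.36 = 15.9%. That leaves 102 and 94 of 112.
- Mean standardised z-change residual among those observed: 0.30 × 0.5/(1.36 × 0.912) = 0.121 and 0.30 × 0.703/(1.36 × 0.841) = 0.184. The difference D is 0.0635.
- Attenuation of a complete-case effect: 0.6 × ρ × D/0.315 = 2.4% (ρ = 0.2) to 6.1% (ρ = 0.5).
- Power (noncentral t, 6 df, set to 80% at 112 per arm): 75.8% from lost values alone, and 73.8% to 70.7% with attenuation.

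Over all six combinations of SD and width:

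| Quantity | Range |
|---|---|
| Missing, comparison | 6.8-12.0% |
| Missing, intervention | 12.3-18.8% |
| Attenuation, complete cases | 1.7-6.7% |
| Power, lost values only | 74.7-76.9% |
| Power with attenuation | 68.9-75.5% |

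A separate simulation used a truncated-normal baseline z, z-change SD 0.37, log HOMA-IR SD 0.5 and correlations 0.3 to 0.7. It gave 8.5% and 14.7% missing, and an effect of 0.305 to 0.291 instead of 0.315 (3-8% smaller).

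**4. What the promised methods could absorb.** BMI is measured at year 2 in every student seen. In simulation, imputing HOMA-IR from baseline HOMA-IR, baseline z and year-2 z within arm left a bias of −1.0% to +0.3%. This extrapolates linearly below the cut, where no values would be seen.

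**5. Exclusions at years 1 and 2.** The documents give no rates. A balanced loss of 2% (4-5 of 224) takes 80% power to 79.4%; 5% (about 11) takes it to 78.4%.

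**The case for a change.** The strongest argument for acting is that the authors write baseline explicitly for ACTION eligibility and for the analysis set, yet leave it out of the general sampling sentences. Comparison schools justifies sampling by standard of care, a clinical rationale that fits current status. An undrawn sample is lost for good, and a clarifying sentence costs almost nothing. The imputation variables are unnamed, so the model as written would not correct such a loss.

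The missing time point and the unnamed imputation variables stand as observations. They do not establish a rule that loses data. Every passage that says who contributes two-year blood outcomes points to the baseline cohort, and staff following the plan need those samples to produce the outcome it defines. Nor does the plan keep year-2 BMI out of the imputation.

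A harsher scenario, in which treatment lowers HOMA-IR only through BMI z, cannot support a larger figure. It needs a within-arm slope of 0.315/0.16 = 1.97 log units per z. With the assumed SD of 0.6, the correlation would be 1.97 × 0.30/0.6 = 0.98 at z-change SD 0.30, and impossible values of 1.18 and 1.34 at 0.36 and 0.41.

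On the exclusions, it is true that the documents do not connect them to intention to treat. The annual health history is common to both arms, though. Closer detection of eating disorders through ACTION visits is only a possibility, and neither the direction nor the size of any bias can be shown.

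**Conclusion.** The concern is not upheld as a reason to change the plan. The sampling wording leaves the time point unstated, but the power and analysis sections supply it: the two-year HOMA-IR sample is the cohort overweight or obese at baseline. If that is followed, the 224 stands and nothing is lost. The figures of about 7-12% and 12-19% missing, 2-7% attenuation and 69-76% power apply only if sampling tracked current status. They rest on an assumed baseline z distribution, HOMA-IR SD and correlations; the attenuation, and the power that includes it, also presuppose a complete-case analysis the plan does not propose.

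The pregnancy and eating-disorder exclusions are likewise missing detail. Under the stated intention-to-treat and missing-data approach, the natural handling is to keep these students in their assigned arm, with unmeasured values treated as missing. This conclusion would alter only if Table 1 or the field procedures showed that year-2 bloods were withheld from baseline-overweight students who had fallen below the cut.
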